5.1 Patient inclusion criteria

- Histologically confirmed rectal adenocarcinoma with lower (distal) limit ≤12 cm from the anal verge using rigid sigmoidoscopy
- Rectal Cancer staged with MRI as locally advanced:

Mesorectal fascia threatened (tumour ≤1mm from mesorectal fascia) Mesorectal fascia involved or breached

- Low tumours arising <5cm from the anal verge
- No evidence of metastatic disease
- No pre-existing condition which would deter radiotherapy, e.g. fistulas, severe ulcerative colitis (particularly patients currently taking sulphasalazine), Crohn's disease, prior adhesions
- Estimated GFR (using Cockroft-Gault formula) >50 ml/min. If this is less than 50ml/min a 24-hour urine collection for estimation of GFR is required or a serum EDTA clearance
- Absolute neutrophil count ≥ 1.5 x 10⁹/I. Platelets ≥ 100 x 10⁹/I, serum bilirubin <1.25 x upper limit of normal (ULN); serum transaminase(s) < 3 x ULN; serum ALP < 5 x ULN
- Fit to receive all study treatments
- Able to comply with oral medication
- WHO performance status 0 or 1
- Written informed consent

5.2 Patient exclusion criteria

- Previous chemotherapy
- Previous radiotherapy to the pelvis
- Patients who have very significant small bowel delineated within the radiation fields
- Current or impending rectal obstruction (unless de-functioning stoma present), metallic colonic rectal stent in situ
- Pelvic sepsis
- Uncontrolled cardiac, respiratory or other disease, or any serious medical or psychiatric disorder that would preclude trial therapy or informed consent
- Known dihydropyrimidine dehydrogenase deficiency
- Pregnant, lactating women or potentially childbearing patients not using adequate contraception
- WHO performance status of 2 or more
- Gastrointestinal disorder which would interfere with oral therapy or oral bioavailability.
- Patients who are deemed unsuitable for surgery because of co-morbidity or coagulation problems.
- Participation in other studies except genetic studies such as NSCCG (National Study of Colorectal Cancer Genetics)
- Patients taking St. John's Wort

6 Investigations Before Registration

To confirm eligibility, the patients must have had the following investigations and assessments prior to registration (data from routine investigations can be used):

- Diagnostic histology
- MRI to stage the disease (within 35 days of registration)
- Liver imaging and chest x-ray to exclude metastatic disease
- FBC, U&Es, LFTs
- Estimated GFR using Cockcroft-Gault Formula (See Appendix 4)
- Pregnancy test if applicable
- Clinical examination including height, weight, vital signs and WHO performance score (see Appendix 2)

7 Registration Procedure

Following a verbal and written explanation of the study, consenting patients will be registered as follows:

- Contact Cancer Research UK & UCL Cancer Trials Centre to check eligibility.
- Allocation of trial number.

A confirmation fax will then be sent to the recruiting site and pharmacy.

REGISTRATIONS

Mon to Fri 9am to 5pm

[contact]

8 Study Design/Treatment Protocol

8.1 Overall study structure

This is a multi-site phase II enrolment study. Centres participating in the study will include the four North West centres in the NWCOG, plus up to four others.

THE PRIMARY ENDPOINT is the histologically confirmed R0 resection rate.

THE SECONDARY ENDPOINTS are as follows:

- Radiotherapy compliance.
- Grade 3 or 4 toxicity.
- Pathological complete response
- Morbidity post operative and long term.
- Disease-free survival and local failure-free survival.

Patients will be assessed for eligibility prior to recruitment (see inclusion/exclusion criteria).

Treatment should be started as soon as possible after registration. The MRI scan that has been used for eligibility and disease evaluation needs to be within 35 days of registration. Patients should have an acceptable haematological and biochemical profile within 7 days of the first day of chemotherapy administration.

If blood tests and calculated GFR used to confirm eligibility are not within 7 days of treatment start, further testing will be required (see Section 9 for details). If the following were not included in routine investigations prior to registration, they too need to be obtained prior to the start of study treatment as part of the required baseline investigations: CEA, serum magnesium, clotting (see Section 9)

A calculated glomerular filtration rate (GFR) using the Cockroft Formula is acceptable but if this is less than 50 ml/min then a formal 24-hour urine collection or serum EDTA clearance should be carried out to determine GFR (see Appendix 4).

Before CRT begins, 2×10 ml blood samples will be collected from consenting patients. One sample will be used for testing for UGT1A1 polymorphisms and the other will be stored for future research studies (see Section 19). Patients will receive a six week (in total) course of treatment: week 1, cetuximab only; weeks 2 - 6 radiotherapy combined with cetuximab, irinotecan and capecitabine.

A defunctioning stoma will be fashioned for severe symptoms due to the primary tumour at the discretion of the treating team.

A clinical evaluation will be carried out (doctor/nurse) at the commencement of cetuximab, every week during radiotherapy and for four weeks following completion of treatment to record blood count, biochemical profile, estimated GFR, and toxicity scores (using NCI CTC V.3.0). Serum magnesium is to be monitored weekly for 8 weeks post completion of cetuximab treatment. In patients on anticoagulants or those with an abnormal initial clotting profile, clotting profile is measured weekly during chemotherapy then weekly for four weeks post-termination (and longer if deemed clinically appropriate) if this is abnormal.

An MRI scan will be carried out at six weeks following radiotherapy completion then an attempt at surgery will take place eight weeks post radiotherapy completion.

Following surgery, adjuvant chemotherapy is given according to the discretion of the treating physician but recorded on the relevant CRF.

A sample of formalin-fixed paraffin-embedded tumour tissue removed during surgery will be sent to a central lab for analysis of KRAS mutation status. The tumour tissue will be stored and used in future research studies if the patient has consented to this. Otherwise, it will be returned to the site.

From the point of view of late toxicity, patients will be assessed at 6, 12, 24 and 36 months post completion of radiotherapy.

On confirmed tumour progression further formal follow-up within the trial ceases apart from ultimately recording date and cause of death. Further clinical management, including second-line chemotherapy is at the discretion of the treating physician. On study withdrawal for any reason then the CRF Off Study Form is completed, providing reason for treatment withdrawl and/or complete withdrawl. On patient death, CRF Death Form is (also) completed.

No other concomitant cytotoxic treatment or radiotherapy is permitted during the trial.

Specified dose limiting toxicities:

All toxicities below must adhere strictly to definitions specified in the National Cancer Institute Common Terminology Criteria for Adverse Events v3.0:

 Grade 3 diarrhoea that does not improve to grade 2 or less, within 24 hours on intensive anti-diarrhoeal therapy

- o Grade 4 diarrhoea
- Grade 3 or 4 fatigue
- Grade 3 or 4 neutropenia accompanied by fever (>38°C) or ≥grade 3 infection
- Grade 4 thrombocytopenia (platelet count < 25×10^{9} /L)
- o Grade 4 nausea/vomiting despite full antiemetic treatment
- Grade 3 or 4 palmar-plantar erythrodysesthesia (Hand Foot Syndrome).
- Dose delay of > 2 weeks because of drug-related toxicity.

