8.2 Treatment details

8.2.1 Treatment summary

Patients will be treated with pelvic radiotherapy to a planned volume at a dose of 45 Gy in 25 daily fractions of 1.8 Gy treating 5 days per week from Monday-Friday.

Concurrently they will receive oral capecitabine at 650 mg/m² bd 5 days per week from Monday-Friday on the days of radiotherapy only.

In addition, they will receive a loading dose of iv cetuximab at 400 mg/m² one week before the commencement of radiotherapy then at 250 mg/m² once per week during weeks 1, 2, 3, 4 and 5 radiotherapy i.e. six doses of cetuximab in total.

In addition they will receive iv irinotecan at 60 mg/m² once per week for four doses in total during weeks 1, 2, 3 and 4 of radiotherapy. Administration of irinotecan follows the administration of cetuximab.

Antiemesis: Prior to weekly treatments including iv irinotecan and cetuximab it is recommended that patients will receive premedication using a 5HT3 antagonist such as 8 mg iv ondansetron plus a steroid such as 8 mg iv dexamethasone (in addition they will receive an antihistamine such as 10 mg iv chlorpheniramine to reduce the likelihood of a cetuximab-related infusion reaction). Prior to treatment with iv cetuximab alone, it is recommended that patients receive an antihistamine plus steroid. Oral antiemetics following iv infusions including irinotecan might include dexamethasone for one or two days but otherwise antiemetics such as metaclopramide or domperidone are to be used as required according to standard local practice.

Patients may have a Hickman line or peripherally inserted central catheter (PICC) inserted at the physician's discretion if required to give adequate venous access for the administration of cetuximab and irinotecan. In these patients prophylactic warfarin should not be given because of the interaction between warfarin and capecitabine. Body surface area (BSA) will be calculated using actual body weight and no dose capping is carried out. No change in the dose calculation is carried out for obese patients.

No dose banding is carried out for irinotecan or cetuximab although it is for capecitabine (detailed in Section 8.2.2).

Instructions for storage use and handling of each drug should be according to each SmPC and hospital policies.

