8.4.6 Cetuximab: Dose modification and treatment for hypomagnesemia

Hypomagnesemia has been reported in up to 65% of patients following cetuximab therapy. Fatigue, malaise, tremor, ataxia, carpopedal spasm, hyperreflexia, confusion, hallucinations, convulsions and arrhythmias may occur.

Patients should have magnesium concentration monitored at baseline, prior to each cycle of chemotherapy and for up to 8 weeks after the last dose of chemotherapy, or until magnesium has normalised, whichever is the longer. Hypomagnesemia should be corrected by intravenous supplementation if grade 3 (<0.4 mmol/l) or symptomatic. If lesser degrees of hypomagnesemia are detected, oral supplementation may be considered

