9.1.3 Post chemoradiation

Weekly for 4 weeks

- FBC, U&Es, LFTs
- Serum Magnesium (continue for 8 weeks in total or until magnesium has normalised; whichever is the longer)
- Toxicity assessment (using NCI CTCAE v3.0)

6 weeks post chemoradiation

- CEA
- Pelvic MRI scan

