9.4 Assessment flowchart

	Pre Reg	Wk 1	Wk	post	Mon	ths aft	er end	CRT												
	Therkey	VVKI	2	3	4	5	6	7	8	9	10	11	12	13	14	ор	6	12	24	36
Radiotherapy								•												L
E Cetuximab								•												
E Capecitabine								•												
≝_ Irinotecan							→													
Surgery															X					
Physical exam	X																X	X	Х	X
Vital signs	X	X	X	X	X	X	X													
Height & weight	X																			
g WHO	X																			
Capecitabine compliance			X	Х	X	X	X													
FBC	X	X	X	X	X	Х	X	X	X	X	Х									
. Clotting profile	X																			
U+E+creat	X	X	X	X	X	Х	X	X	X	X	Х									
ਚੁੱ Magnesium	X	X	X	Х	X	Х	Х	Х	X	X	Х	Х	Х	Х	Х					
	X	X	X	X	Х	Х	X													
S LFT	Х	Х	X	Х	X	Х	X	Х	Х	Х	Х									
E Histological confirmation	Х																			
CEA CEA	Х												X							
Liver (US or CT)	Х																			
A MRI pelvis	X												X							
CXR	X																			
Toxicity	X	X	X	X	X	Х	X	X	X	X	Х						Х	Х	Х	X
Consent form	X																			
Collection of diagnostic tissue block for KRAS testing																				
Ancillary study blood samples x 2 (optional)	X																			
Registration/baseline CRF	X																			
는 Copy of baseline MRI	X																			
E Treatment CRF		X	X	Х	X	Х	X	Х	X	X	Х									
Post treatment summary CRF													X							
Copy of post CRT MRI report													X							
g Surgery CRF																X				
Copy of histology report																X				
Follow-up CRF																	Х	Х	Х	X

In this chart Week 1 is the week in which cetuximab alone is given and Week 2 is the week in which radiotherapy is started.

Serious Adverse Event Forms, Patient Withdrawal Form and Death Form to be completed as needed.

Figure 11: Flowchart for assessments and CRF completion

10 Withdrawal of Patients

In consenting to the trial, patients are consenting to trial treatment, trial follow-up and data collection. If a patient wishes to withdraw from trial treatment, institutions should nevertheless explain the importance of remaining on trial follow-up, or failing this of allowing routine follow-up data to be used for trial purposes.

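### Serum magnesium monitoring has a fixed end in Protocol section 8.1 and Figure 11 but runs until normal in sections 8.4.6 and 9.1.3, and its clock starts from three different events

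*Protocol*

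**What the plan says.** Four places in the protocol govern how long serum magnesium is followed after treatment.

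- **Section 8.1, Overall study structure:** "Serum magnesium is to be monitored weekly for 8 weeks post completion of cetuximab treatment". The period is fixed and counted from the end of cetuximab.
- **Section 8.4.6, hypomagnesaemia:** monitoring runs "for up to 8 weeks after the last dose of chemotherapy, or until magnesium has normalised, whichever is the longer".
- **Section 9.1.3, Post chemoradiation:** "Serum Magnesium (continue for 8 weeks in total or until magnesium has normalised; whichever is the longer". The section heading makes the end of chemoradiation the starting event.
- **Section 9.4, Figure 11:** the magnesium row has a mark at pre-registration and in each of weeks 1 to 14. It has none in the post-operative or month 6 to 36 columns, and no note extends it.

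Two further statements set the timing. Section 8.2.1 gives cetuximab "once per week during weeks 1, 2, 3, 4 and 5 radiotherapy i.e. six doses of cetuximab in total", and section 8.1 says that "an attempt at surgery will take place eight weeks post radiotherapy completion".

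**The concern.** Two places end routine testing at a set time. Two require it to continue while the value is abnormal. For a patient whose magnesium is still low at week 14, a site gets opposite instructions depending on the page it works from.

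Section 8.1 can fairly be read as a fixed stop. Its next sentence lets clotting tests go on longer on clinical judgement, and the magnesium sentence has no such allowance.

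The starting events differ as well. This matters when cetuximab ends before the rest of treatment, which the protocol foresees: section 8.4.4 requires permanent discontinuation after a severe infusion-related reaction, and section 8.4.3 after more than two consecutive withheld infusions.

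What is at stake is safety follow-up of a known cetuximab effect. Section 8.4.6 says that "Hypomagnesemia has been reported in up to 65% of patients following cetuximab therapy" and lists convulsions and arrhythmias among the possible effects. Duration and recovery could also be recorded differently from site to site. In Figure 11 the weekly toxicity assessment stops at week 10 and the next is at month 6. Magnesium is the only blood test still scheduled every week between those points, so other planned visits are unlikely to show up a lapse.

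**Working it through.** The protocol gives no figure to reproduce. The check is a comparison of the stopping rules, followed by day counts on the planned schedule.

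**1. Stopping rule and starting event**

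| Place | Clock starts at | Ends at | Extended if still abnormal? |
|---|---|---|---|
| 8.1 | completion of cetuximab | 8 weeks | not stated |
| Figure 11 | not tied to an event | week 14 | not stated |
| 8.4.6 | last dose of chemotherapy | 8 weeks | yes, until normal |
| 9.1.3 | end of chemoradiation | 8 weeks | yes, until normal |

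**2. Inputs for the day counts**

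- Section 1.3: the loading dose is on day 1, radiotherapy starts on day 8, and its last week is days 36 to 40. Figure 11 agrees that "Week 2 is the week in which radiotherapy is started".
- Section 8.2.1: the last planned cetuximab dose is in radiotherapy week 5 (days 36 to 40). The last irinotecan dose is in radiotherapy week 4 (days 29 to 33).
- Section 8.2.2: capecitabine runs to the last radiotherapy day, day 40.
- Eight weeks is 56 days. Trial week = whole part of (day − 1)/7, plus 1.

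**3. All treatment given to schedule**

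- Cetuximab clock (8.1): 36 + 56 = 92 to 40 + 56 = 96, so days 92 to 96, week 14.
- End-of-chemoradiation clock (9.1.3): 40 + 56 = day 96, week 14. It ends 0 to 4 days after the cetuximab clock.
- Last-chemotherapy clock (8.4.6), read as capecitabine: day 96, week 14. Read as irinotecan: 29 + 56 = 85 to 33 + 56 = 89, so days 85 to 89, week 13.
- Planned surgery: 40 + 56 = day 96, week 14.

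On schedule, therefore, the starting events hardly matter. The difference lies in whether testing continues after about week 14 when magnesium is still low.

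**4. Cetuximab stopped at the loading dose, other treatment to schedule**

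- 8.1: 1 + 56 = day 57, week 9.
- Against 9.1.3: 96 − 57 = 39 days (week 9 against week 14, about 5 weeks).
- Against 8.4.6 read as capecitabine: the same 39 days. Read as irinotecan: 85 − 57 = 28 to 89 − 57 = 32 days (week 9 against week 13, about 4 weeks).

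For this patient 8.1 also disagrees with Figure 11, which still shows tests to week 14. Figure 11 then matches the 9.1.3 minimum.

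**The case against.** The strongest reply is that the two detailed instructions agree. The hypomagnesaemia section and the assessments section both extend testing until normal, whereas 8.1 is an overview. Its 8 weeks could be read as a minimum, since it does not say that testing stops when the value is abnormal. The advice on correcting low magnesium is also in 8.4.6, next to the extension, so a clinician dealing with a low value is likely to meet it there. This lowers the chance of harm. It does not remove the conflict, because 8.1 neither refers to the extension nor uses the same starting event.

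Figure 11 is the weaker of the two fixed-end sources. It is a grid of scheduled visits and does not carry conditional tests: its clotting row has only a pre-registration mark, although 8.1 and 9.1.2 require weekly clotting for some patients. Its silence is an omission to repair rather than a competing rule. It is also not tied to cetuximab.

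Safety recording does not depend on this schedule alone. Section 15.1 counts abnormal laboratory findings as adverse events, section 15.2.1 has them recorded to 36 months after chemoradiation, and serious events are followed to resolution. That stands, although when a low value recovered can only be known if it is measured. Section 9.1.5 also allows other tests at the clinician's discretion, which is less than the requirement in 8.4.6 and 9.1.3.

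Two stronger readings are tempting, and the documents support neither.

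- A reader might infer that patients in general lose monitoring before surgery. For a patient on schedule, every version covers the interval to about the planned operation, and the last Figure 11 mark is in the surgery week.
- A reader might apply the 65% to the 80 planned patients (0.65 × 80 = 52) and take 52 as the number affected. The 65% is an upper figure for any hypomagnesaemia, not for patients still abnormal when the fixed window closes.

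**Conclusion.** The inconsistency is real but small. Section 8.1 and Figure 11 lack the until-normal extension that 8.4.6 and 9.1.3 require, and the clock has three different starting events.

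It affects two groups: patients whose magnesium is still abnormal after week 14, and patients who stop cetuximab early at a site following 8.1 alone. The protocol does not give the share still abnormal at 8 weeks or the expected rate of early cetuximab cessation, so the size of either group cannot be derived.

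In the extreme case of cessation at the loading dose, the 8.1 window closes 39 days before the 9.1.3 window and 28 to 39 days before the 8.4.6 window. That range depends on which drug counts as the last chemotherapy. The counts assume that the remaining treatment runs to the planned days without interruption.

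The point concerns safety follow-up and the consistency of toxicity data. It has no effect on the primary endpoint or the sample size, and it belongs at the lowest severity.

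**What to change.** Reconcile sections 8.1, 8.4.6, 9.1.3 and Figure 11 so that all four give the same starting event and the same end point for magnesium monitoring. State what applies when cetuximab stops before the rest of chemoradiation. If the clock is to run from the last dose of chemotherapy, say which drug is meant. A footnote to the magnesium row is enough for Figure 11. Which rule applies is for the clinical team to decide.

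The cost is a few words in the text and one footnote. The test is already being done, so the change adds at most a few serum samples.

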8.1.4 Post-surgery

• Send tumour tissue blocks for KRAS testing (see Section 19)

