9.2 Efficacy endpoints

Resectability will be defined in terms of:

- R0 resection rate i.e. the carcinoma is resected with margins clear by >1mm.
- R1 resection rate i.e. the carcinoma has microscopically-involved margins
- R2 resection rate i.e. the carcinoma is resected but has macroscopically-involved margins at the time of surgery.

Response rate will be defined in terms of:

• Pathological complete response (pCR) i.e. no residual viable carcinoma on extensive examination of the resected specimen.

The following will also be recorded:

- 'Near' pCR i.e. microscopic foci of occasional single carcinoma cells remaining on extensive examination of the specimen.
- Decrease in size of the carcinoma in superior-inferior and transaxial dimensions on comparing pre- and post- CRT MRI scans.
- Change in MRI-defined TNM stage of tumour on pre- and post-CRT MRI scans.
- TNM stage of resected specimen compared to predicted on pre-CRT MRI scan.

The denominator will be total numbers of subjects recruited for the trial and commencing CRT treatment.

The following categories of patient will be distinguished:

- Patients undergoing CRT and an attempt at laparotomy but tumour not resected because found to be too locally advanced at surgery.
- Patients undergoing CRT and an attempt at laparotomy but tumour not resected because found to have developed metastatic disease.
- Patients undergoing CRT and an attempt at laparotomy but tumour not resected because of other reasons.
- Patients undergoing CRT but not undergoing surgery because tumour remains too locally-advanced on restaging MRI.

Disease free survival - the 'event' will be time from randomisation to confirmation of local failure or recurrence, distant metastases, or death from any cause, whichever occurs first, disease-free patients being censored at the date last seen.

Local failure – A local failure is defined as:

- pelvic disease extent is considered unresectable (after pre-op CRT has been given and reassessment has taken place).
- when at laparotomy there is residual macroscopic pelvic malignancy.
- when during the follow up period (after macroscopic clearance of tumour was achieved) there is evidence of confirmed local recurrence. Confirmed local recurrence includes biopsy confirmation of local recurrence, unequivocal local recurrence on imaging (MRI scanning and /or PET) or equivocal local recurrence on imaging in the definite absence of metastatic disease and in the presence of a rising CEA.

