If the results indicate that the R0 resection rate is consistent with a true rate of at least 75% then the proposed regimen is deemed worthy of further investigation in a future phase III trial. The R0 resection rate is about 50-60% in the intention-to-treat population using single agent fluoropyrimidine (5FU or capecitabine) as a radiation sensitiser - we use the midpoint of 55% in the sample size calculation. With the addition of irinotecan and cetuximab we expect this to increase to at least 75%. Using a Fleming's design with 80% power (and one-sided test of statistical significance at the 5% level), 35 patients would be required. Initially the recruitment target was 40 patients, which would allow for some drop-outs, this has been updated to 80 patients.

In the NWCOG-2 (RICE) trial and other studies of irinotecan-containing CRT regimes, diarrhoea is the most common serious toxicity. Within RICE 20% of 91 patients suffered grade 3 or 4 diarrhoea (all grade 3 apart from one grade 4). In the proposed study a true grade 3 or 4 diarrhoea rate of more than 30% would be unacceptable (as is standard for chemoradiation studies in pelvic cancers). We will monitor the number of grade 3 or 4 toxicities during the course of the trial. Given the original sample size of 40 patients, we would consider stopping the study early if 17 patients with a grade 3 or 4 diarrhoea were observed, since the probability of this occurring by chance if the true toxicity rate were 30% is 0.03.

Data on toxicity from the first 20 patients followed for at least one month following completion of CRT will be reviewed by an Independent Data Monitoring Committee (IDMC). This analysis, will be performed by the trial statistician and remain confidential to the IDMC. The IDMC will be asked to give advice on whether the trial should stop early because of unacceptable toxicities.

An analysis of the main outcomes will also be carried out, comparing the results of patients based on whether they are found to be KRAS wildtype or KRAS mutant.

The original proposal for EXCITE was based on seeing an increase in the R0 resection rate from 55% when using single agent fluoropyrimidine to 75% with the addition of irinotecan and cetuximab. This would have required 35 patients to achieve 80% power, using a Fleming's design, and the aim was to recruit 40 patients.

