19.1 Collection of tumour tissue

19.1.1 DNA analysis

For all patients entering the study, formalin-fixed paraffin-embedded (FFPE) tumour tissue samples removed during a routine diagnostic biopsy and at surgery will be collected for DNA EXCITE protocol v4.3; 21st August 2015

analysis. The tissue will be analysed in the laboratory of [name] at Leeds Institute of Molecular Medicine for the presence of mutations in the KRAS and BRAF genes. The results of these analyses will not be used to influence the clinical management of the patient but instead will be used to examine the association of KRAS and BRAF mutations with patient outcome after CRT.

Extracted DNA will be transferred to the laboratory of [name] in the School of Biology, University of Bangor who will examine genetic mechanisms of resistance to irinotecan.

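### The protocol contradicts itself on which tissue sets KRAS status, and one of its readings would make membership of the wild-type R0 analysis depend on outcome

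*Protocol*

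**What the plan says.** Four places in the protocol deal with tissue for KRAS testing.

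- **Section 8.1** names one source: "A sample of formalin-fixed paraffin-embedded tumour tissue removed during surgery will be sent to a central lab for analysis of KRAS mutation status".
- **The post-surgery list in Section 9.1** (printed as 8.1.4) has the instruction "Send tumour tissue blocks for KRAS testing (see Section 19". The baseline list in Section 9.1.1 has no tissue item.
- **The Section 9.4 flowchart** has a row reading "Collection of diagnostic tissue block for KRAS testing". Its time point cannot be read in the text available, and I draw nothing from that.
- **Section 19.1.1** says that, for all patients entering, "tumour tissue samples removed during a routine diagnostic biopsy and at surgery will be collected for DNA" analysis, and that the tissue is examined "for the presence of mutations in the KRAS and BRAF genes".

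Three further statements matter. Inclusion requires "Histologically confirmed rectal adenocarcinoma" (Section 5.1), so pre-treatment tissue should exist for everyone. For the efficacy endpoints, Section 9.2 states: "The denominator will be total numbers of subjects recruited for the trial and commencing CRT treatment". Section 13 gives evaluation of R0 in KRAS wild-type tumours as the whole reason for the increase to 80 patients, with a 97% chance of at least 40 such tumours.

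**The concern.** Read alone, Section 8.1 ties KRAS typing to having had a resection. On the Section 9.2 denominator, a patient who starts CRT and is never resected is an R0 failure. Under Section 8.1 that patient has no specimen, cannot be called wild type, and leaves the analysis because of the primary outcome. A patient with pathological complete response has, by the Section 9.2 definition, no viable carcinoma left to type, and leaves because of a good outcome.

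The wild-type R0 rate would then no longer be on the same footing as the 55% benchmark, which Section 2.3 and Section 13 place on all patients who started treatment. The number of typed wild-type patients would also shrink.

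Section 19.1.1 and the flowchart point the other way. With no order of precedence, sites working from Sections 8 and 9 could send different tissue from sites working from Section 19.

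**Working it through.** **Inputs.** Section 13 gives null R0 rate 0.55, target 0.75, one-sided 5%, power 80%, wild-type prevalence 0.60, and at least 40 of 80 wild type. Section 2.5 (predecessor regimen) gives 7 of 81 unresected (8.6%) and 19 complete responses, which is 23.5% of 81; the printed 29% is 19/65. Section 2.3 (single-agent CRT) gives 13% complete response, applied here to all patients starting CRT.

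**Assumptions.** KRAS status is independent of resection and response. Every complete responder is R0 and untypable from the surgical block. The go rule is at least 28 of 40, which the protocol does not state. It is the smallest exact cut-off with error at or below 5% at a rate of 0.55: 28 gives 0.039 and 27 gives 0.075. Its power at 0.75 is 0.82.

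**The plan's own figures reproduce.**

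- Sample size: [(1.645√(0.55×0.45) + 0.842√(0.75×0.25)) / 0.20]² = 34.97, so 35.
- P(Bin(80, 0.60) ≥ 40) = 0.973, stated as 97%.

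**Surgical tissue only.** Let u be the share unresected and c the share with complete response that cannot be typed.

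- Share typed: f = 1 − u − c
- Chance of enough wild-type tumours: P(Bin(80, 0.60f) ≥ 40)
- Apparent R0 rate when the truth is 55%: (0.55 − c)/(1 − u − c)
- False-go rate: P(Bin(40, apparent rate) ≥ 28)

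| Lost from typing | f | 0.60f | Expected typed wild type | P(≥40) | Apparent R0 | False-go |
|---|---|---|---|---|---|---|
| Nobody (biopsy used) | 1 | 0.600 | 48.0 | 0.973 | 55.0% | 0.039 |
| Unresected, 7/81 | 0.914 | 0.548 | 43.9 | 0.836 | 60.2% | 0.134 |
| Unresected plus 13% complete response | 0.784 | 0.470 | 37.6 | 0.336 | 53.6% | 0.026 |
| Unresected plus 19/81 complete response | 0.679 | 0.407 | 32.6 | 0.059 | 46.5% | 0.002 |

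For example, row two is 0.55/0.914 = 0.602, and row three is (0.55 − 0.13)/0.784 = 0.536.

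**Where the bias changes sign.** Setting (0.55 − c)/(1 − u − c) = 0.55 gives c = 0.55u/0.45. With u = 7/81 = 0.0864, c = 0.106. Below about 10.6% untypable complete responders the apparent rate is too high; above it, too low. The protocol quotes complete response rates on both sides: 5% and 8% in Phase II-type studies of cetuximab-containing CRT (Section 2.8), 13% and 23.5% as above.

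**The case against.** The best defence is that the section devoted to biological studies already settles the matter. Section 19.1.1 takes biopsy and surgical tissue from everyone for KRAS testing, Section 19.1.3 again mentions samples from either source, and the flowchart names the diagnostic block. Section 8.1 is an overview and does not say that surgical tissue is the only source. The post-surgery item does not say surgical blocks, and it refers to Section 19, so it can be read as fixing when blocks are sent and not which ones.

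Most of this stands. A reader might infer from Section 8.1 that the plan excludes unresected patients and complete responders from the wild-type analysis. The documents do not support that, because it follows only if Section 8.1 is applied over Section 19.1.1.

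A reader might also infer that the false-go rate is inflated, taking the 13% alone. That figure covers loss of unresected patients only. Losing complete responders as well pulls the rate down, in two of the scenarios to below the 3.9% of the intact rule. Nor must the wild-type count fall short of 40: in the unresected-only case the chance of reaching it is still 84%.

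What the defence does not answer is the conflict itself. Section 19.1.1 collects two specimens without ranking them. The only instruction in the Section 9.1 visit lists to send blocks comes after surgery, an event some patients never reach. A statistical analysis plan may exist and may choose a specimen, but it cannot supply blocks that sites were not told to send.

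**Conclusion.** The contradiction is real and needs reconciling. It is a conflict of wording with no rule of precedence, not an established design that discards patients. It matters because one reading makes KRAS typing depend on the primary outcome, in the one analysis that justifies 80 patients.

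If that reading were followed, the chance of 40 typed wild-type tumours would drop from 97% to between 84% and 6%. A true 55% could appear as anything from 60% down to 46.5%, with the false-go rate anywhere from 13% to 0.2% against 4%. The direction of the bias is not determined. These sizes rest on frequencies borrowed from earlier regimens, on independence of KRAS status from outcome, on all complete responders being R0 and untypable, and on a 28-of-40 cut-off supplied here. If Section 19.1.1 is followed and the biopsy is typed, the effect is nil.

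**What to change.** - Amend Section 8.1 and the post-surgery list to agree with Section 19.1.1 and the flowchart.
- State that KRAS status for the R0 analysis comes from the pre-treatment diagnostic biopsy for every patient commencing CRT, with the surgical block used only if the biopsy fails.
- Ask sites for the diagnostic block whether or not surgery takes place, and add this to the baseline list.
- Report the number of untyped patients by resection status and pathological response, so that any remaining selection is visible.

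The cost is mainly wording: Section 19.1.1 already provides for collecting the biopsy tissue, and KRAS results do not affect patient management. The small downside is that some biopsies may yield too little DNA. The back-up rule covers those patients only if they were resected with viable tumour remaining, which is why the report of untyped patients is needed.
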